#### 1.3 Hypotheses

The study will address the following hypotheses:

- 1. Children with mild to moderate chronic kidney disease secondary to structural causes have slower rates of declining GFR compared to those with acquired glomerular disease.
- Accelerated CKD progression will be associated with a positive family history of kidney disease, black race, Hispanic ethnicity, lower socioeconomic status, elevated systolic and diastolic blood pressure, high nocturnal blood pressure, anemia, periods of accelerated growth, hyperparathyroidism and hyperlipidemia.
- 3. When indicated, early surgical intervention as well as the prescription and adherence to therapy with angiotensin converting enzyme inhibitors, angiotensin receptor blockers and aldosterone inhibitors will slow CKD progression.
- 4. Systematic measurements of GFR, centrally measured "true" serum creatinine, centrally based serum Cystatin C and comprehensive clinical data will yield GFR estimating equations with better accuracy

and more precision than current formulas based on height and serum creatinine.

- 5. Declining GFR will be associated with measurable declines in neurocognitive function, behavior and quality of life in children with CKD. The greatest deficit in cognitive function will be seen in children with the longest duration of CKD, the highest stage of CKD and with the lowest hemoglobin levels.
- 6. Progressive CKD will adversely affect central nervous system conduction pathways, and detectable anatomic changes (white matter changes) will correlate with changes in neurocognitive status and GFR.
- 7. The prevalence and severity of traditional cardiovascular disease (CVD) risk factors (hypertension, hyperlipidemia) and uremia-related CVD risk factors (inflammation, malnutrition, anemia, hyperparathyroidism), will be associated with the progression of CKD.
- 8. The prevalence and severity of systemic and nocturnal hypertension will be associated with the decline of GFR and the development of concentric left ventricular hypertrophy (LVH). The prevalence and severity of anemia will be correlated with GFR decline and the development of eccentric LVH.
- 9. LVH will be responsible for decreased LV diastolic function in children with CKD.
- 10. Decreased aortic wall compliance will be related to elevated systolic blood pressure, hyperlipidemia, biomarkers of inflammation and increased Ca x P product.

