The cardiovascular component will be implemented after the second year and every four (4) years thereafter. The cardiovascular outcomes will be measured while the participants wait for their blood to be drawn for GFR measuring. The same temporality of GFR levels and changes preceding the cardiovascular data (i.e., ECHO) will be provided by our proposed design. The only limitation for the study is that, for Cohort 2, half of the cohort will have only one assessment of cardiovascular risk factors by 2018.

The core markers of neurocognitive function and growth will be measured in the odd years from the third year on. A salient feature of the proposed contact pattern is that the assessment of neurocognitive function will not be perturbed by the requirements of the GFR protocol. The pattern outlined in the table will also be conducive to assessing the impact of the changes in GFR on the changes in neurocognitive function. Specifically, the changes in GFR between year 1 (0 to 12 months) and year 2 could be predictive of the changes in neurocognitive function between year 1 (with a desired lag of six months) and year 3. In addition, the two years in between the assessment of neurocognitive function will minimize practice learning and thus allow a more direct assessment of the impact of kidney disease on neurocognitive development. Finally, the growth component of the study will be conducted at the same time as the neurocognitive component.

In summary, three features of the proposed contact pattern merit emphasis: (i) the GFR measurement in the first two years will provide a measure of GFR change early in the study and it will serve as a good baseline measurement for the long-term change of

GFR; (ii) the availability of concurrent data on GFR and serum creatinine will provide data to develop an internally valid formula which will, in turn, provide the means to complete GFR data by estimating GFR in the odd years; and (iii) both level and changes in GFR will temporally proceed the measurement of the markers of neurocognitive function, cardiovascular risk factors and growth failure.

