## 6.2.1.3 Creatinine Based Estimates of GFR

## 6.2.1.3.1 Original Schwartz Formula

Originally, [Schwartz 1976] developed a formula to estimate GFR from the plasma Creatinine and body length, using an empirically derived constant, k. The value of k is 0.45 for males and females 12 months to 18 months [Schwartz 1984], 0.55 for males between 19 months and 13 years (before 13th birthday) and females 19 months and older [Schwartz 1976], and 0.7 for males after 13th birthday [Schwartz 1985]. This formula generally provides a good estimate of GFR (r ~ 0.9) when compared with Creatinine and inulin clearance data [Hellerstein 1998,Schwartz 1976]. However, the variation between inulin clearance and GFR estimated by Schwartz formula is about 20%-30% [Hellerstein 1998, Schwartz 1976]. Creatinine based estimates of GFR using the Schwartz formula allow for reliable detection of only substantial progression of kidney disease (>25-50% decline in GFR). We therefore used iohexol GFR and serum creatinine to derive a GFR estimating equation that is based on easily obtained demographic and biochemical data that is applicable to the entire CKiD study population.

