## 6.2.1.3.3 Comparisons of the iGFR and the eGFR

Comparison of the relationships between the iGFR and the eGFR (based on the formula published in Kidney International 2012 by Schwartz et al. and the updated bedside formula published in JASN 2009 by Schwartz et al.) with biomarkers of CKD severity has shown that the eGFR reproduces the same epidemiologic inferences as the iohexol GFR. The array of CKD-related biomarkers examined included proteinuria, hemoglobin, bicarbonate, potassium, phosphate, and SBP, DBP and height z-scores. In separate regression models by iGFR and eGFR, we described the effect of a 50% decline on the biomarker of interest (dependent variable). Overall, the eGFR yielded the same epidemiologic inferences as iohexol GFR, with most markers having a stronger relationship with eGFR than iGFR. Further comparisons using the updated bedside GFR [Schwartz 2009] indicated that the associations with the bedside GFR equation (bedGFR) were comparable with the iGFR, although slightly attenuated, which was expected as the bedside formula is only based on height and serum creatinine. In addition to the estimated GFR, the bedGFR will be reported for all participants.

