#### 6.2.1.4 Cystatin C

Cystatin has recently been proposed as a valuable marker of renal function, but this has not yet been validated in a large scale epidemiological study. Cystatin C is a nonglycosylated 13.3-kDa basic protein produced by all nucleated cells. The production rate is not altered by inflammatory conditions or diet. The structure of the cystatin C gene and its promoter indicate that the gene is of the house-keeping type. The low molecular mass of cystatin C in combination with the stable production rate suggests that the major determinant of serum cystatin concentration is glomerular filtration rate. During the last ten years there have been many research abstracts and published papers describing the normal levels of cystatin C and comparing cystatin C with serum creatinine as a parameter for GFR [Bökenkamp 1998, Coll 2000, Filler 1997, Fischbach 2002, Hoek 2003,Laterza 2002, Martini 2003, Newman 1995, Norlund 1997, Randers 2000, Randers 1999].

The methods of the cystatin C assay as well as the estimation of clearance in these patients have been varied. A meta-analysis comparing  $P_{cyst c}$  with  $P_{Cr}$  as a marker for kidney function was based on articles published as of December 31, 2001, and on conference abstracts from annual meetings of the American Society of Nephrology until December 2001 [Dharnidharka 2002]. The authors concluded that the meta-analysis data showed  $P_{cyst c}$  was superior to  $P_{Cr}$  as a marker for GFR.

However, the medical literature remains controversial as to whether  $P_{cyst}$  c is significantly better as a parameter than  $P_{cr}$  for detection of decreased GFR [Dussol 2002]. The comparison of these two markers of renal function will not be resolved until there are studies comparing  $P_{Cr}$  and  $P_{cyst C}$  using standard reference methods for GFR, guidelines for the assay of  $P_{Cr}$  and  $P_{cyst}$  c and for the cystatin C calibrator. We will include each of these measures at baseline and at all annual study visits.

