# 8.2.1 Intelligence Quotient

The intelligence quotient (IQ) is a general and stable indicator of general cognitive functioning that will be validly and reliably measured on children 30 months and older in CKiD. Let  $Y_{ij}$  be the IQ as derived from the WPPSI-III for children aged 30 months to 5 years, or the WASI for children aged 6 to 18 years for child i at visit j, where visit j is taken at time t.

A regression of the form  $Y_{ij} = b_0 + b_1t_{ij} + b_2G_{ij} + b_3G_{ij}t_{ij}$ , where the variable  $G_{ij}$  is the decline of GFR in the preceding year scaled to a 5-unit difference (= (GFRij-1 – GFRij)/5), will describe the trajectory of cognitive functioning as a line with intercepts  $b_0$  for those with no GFR decline and  $b_0 + b_2$  for those with a 5 ml/min|1.73m^2 decline in GFR, and slopes  $b_1$  for individuals who have no GFR decline and  $b_1 + b_3$  for those with a 5 ml/min|1.73m^2 decline in GFR. Here, the intercepts describe the initial difference in IQ due to decline in GFR, and the slopes describe the linear rate of change in IQ due to decline in GFR. Since this study is planning to measure GFR every two years, we will CKiD Protocol 91 06/01/16 to 08/01/17 OSMB Approved

either annualize the change in GFR over the preceding two years for which the observed data will be available or we will estimate the GFR not measured directly in a given year using the serum creatinine which will be available every year. Specifications other than the annual difference in GFR will be explored. Also, we will be able to investigate nonlinear changes in IQ over time by a polynomial expansion of tij into say the cubic function  $t_{ij} + t^{2}_{ij} + t^{3}_{ij}$ . The intrinsic statistical dependence of repeated IQ measurements taken on individuals will either be included as additional parameters using mixed effects models or will be treated as a nuisance using generalized estimating equations.

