## 8.2.3 Linear Growth

Linear growth, as measured by height, is a central component of overall growth that is to be described in this cohort of children. Let  $Y_{ij}$  be the age- and gender-normed standard deviation score (SDS) based on the average of two heights measured in cm for child i at visit j, where visit j is taken at time t. The age- and gender-specific norms are derived as  $Y_{ij} = (U_{ij} - \mu) / SD(\mu)$ , where  $U_{ij}$  is the raw average of the two measured heights,  $\mu$  is the age and gender specific mean norm height and SD( $\mu$ ) is the standard deviation of  $\mu$ ; both  $\mu$  and SD( $\mu$ ) are based on tables provided by the National Center for Health Statistics.

A regression of the form  $Y_{ij} = b_0 + b_1t_{ij} + b_2G_{ij} + b_3G_{ij}t_{ij}$ , where the variable  $G_{ij}$  is the decline of GFR in the preceding year scaled to a 5-unit difference (= (GFRij-1 – GFRij)/5), will describe the trajectory of linear growth as a line with intercepts  $b_0$  for those with no GFR decline and  $b_0 + b_2$  for those with a 5 ml/min|1.73m^2 decline in GFR, and slopes  $b_1$  for individuals who have no GFR decline and  $b_1 + b_3$  for those with a 5 ml/min|1.73m^2 decline in GFR. Here, the intercepts describe the initial difference in height SDS due to decline in GFR, and the slopes describe the linear rate of change in height SDS due to decline in GFR (For more detail about the specification of GFR please see section 8.2.2). As with IQ (see section 8.2.2), we will be able to investigate nonlinear growth rates by a polynomial expansion of  $t_{ij}$ , and the statistical dependence of repeated height measurements will be addressed using either mixed effects models or generalized estimating equations.

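### The growth model in Section 8.2.3 allows a same-visit GFR estimate built from height, so height can enter both outcome and exposure, with a bias of either sign

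*Protocol*

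**What the plan says.** Section 5.4.1 sets the timing: "The core markers of neurocognitive function and growth will be measured in the odd years from the third year on". Iohexol GFR is scheduled at V1a, V2 and the later even visits (Table 5.4.1a). The gaps are to be closed with a formula developed in the study from concurrent iohexol and creatinine data, so as to "complete GFR data by estimating GFR in the odd years". Section 8.2.1 repeats the idea for the IQ model. GFR change may be the annualised change in observed values, or the missing value may be estimated "using the serum creatinine which will be available every year".

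Section 8.2.3 takes height SDS at visit j as the outcome and G = (GFR at j-1 minus GFR at j)/5 as the exposure. The model "will describe the trajectory of linear growth as a line with intercepts" and slopes that depend on G. For the definition of GFR it refers to Section 8.2.2. That is the left ventricular model, which uses a different, earlier GFR interval; the GFR options are in 8.2.1. Section 6.5.3 adds height velocity SDS as a second growth outcome. In the other direction, Hypothesis 2 (Section 1.3) links faster CKD progression to "periods of accelerated growth, hyperparathyroidism and hyperlipidemia", among other factors.

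The creatinine formulas given are the original one (Section 6.2.1.3.1), with k of 0.45, 0.55 "and 0.7 for males after 13 th birthday", and the bedside update (Section 6.2.1.3.2), 0.413 x height in cm / creatinine, with one constant for all ages and both sexes.

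**The concern.** If the GFR at visit j comes from one of the printed formulas, the height that forms the outcome also forms part of the exposure. A child who grows poorly between two visits while creatinine stays put shows a lower eGFR. That looks like GFR decline accompanying growth failure, which Aim 4 sets out to examine. In a pubertal spurt, creatinine may rise faster than height as muscle is gained. The eGFR then falls during rapid growth, which looks like the accelerated-growth part of Hypothesis 2. Neither pattern needs a change in kidney function.

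The exposure as written also conflicts with the stated design. Sections 5.4.1 and 6.5.3 both say that GFR change is assessed before growth, whereas G in Section 8.2.3 runs up to the growth visit itself.

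**Working it through.** **1. The formula is proportional to height.** The example to Table 5.2.1e reproduces: at 84 cm and eGFR 90, creatinine = 0.413 x 84/90 = 0.385, printed as 0.39. At fixed creatinine, a given percentage change in height is the same percentage change in eGFR.

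**2. Height gain with creatinine fixed.** Start at 58, the median initial GFR in Table 9.1 for non-glomerular children with uP/C at or below 0.5. Yearly height gains of 3% to 7% are an assumption.
- 3%: 58 x 0.03 = +1.7 ml/min/1.73m², or 1.74/5 = 0.35 units of G.
- 7%: 58 x 0.07 = +4.1, or 4.06/5 = 0.81 units of G.

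Table 9.1 gives a median change of -1.7 per year in that group, so the shift equals or exceeds the change being studied.

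**3. Creatinine moving with height.** Let true GFR be constant and creatinine vary as height to the power e, so eGFR varies as height to the power (1 - e). For an assumed 5% height gain at 58, the spurious change is 58 x (1.05^(1-e) - 1):

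| e | spurious change (ml/min/1.73m²) |
|---|---|
| 0 | +2.9 |
| 0.5 | +1.4 |
| 1 | 0 |
| 1.5 | -1.4 |
| 2 | -2.8 |

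A simulation with constant true GFR (assumed growth 5%, SD 1.2%; creatinine noise 8%) gave correlations between growth and G of -0.14, -0.07, 0.00 and +0.07 for e = 0, 0.5, 1 and 1.5.

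**4. Upper illustration for boys.** If the original constants were right, height/creatinine at constant GFR would fall to 0.55/0.70 = 0.786 of its value across the 13th birthday. A single-constant formula would read this as a 21% loss: 58 x 0.214 = 12.4, or 12.4/5 = 2.5 units of G. Spread over 1, 2, 3 or 4 years it is 21%, 11%, 8% or 6% per year. Table 9.1 uses 10% per year as its cut. If only half the step is real (assumption), the total is about 11%.

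**5. Availability of iohexol GFR.** Section 6.2.1.1 now continues it only in Cohort 1 and 2 children at or above 90 at their last visit, until they fall below 90, and makes it optional in Cohort 3. In Table 9.1 the upper quartiles of initial GFR are 70, 77, 68 and 61 in the four groups, so at most a quarter of any group started above 77. That most children no longer have an observed GFR is an inference from these figures; the protocol gives no count.

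**6. Planned adjustment.** Tanner stage is recorded at annual visits (Section 6.1.1.2), but the extended model in Section 8.2.3 adds only the share of life lived with CKD and dietary intake.

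**The case against.** The protocol permits a height-based GFR here; it does not require one. Section 5.4.1 names iohexol GFR as the exposure for Aims 2 to 4, and Section 6.2.3.1 makes it the primary renal outcome, which covers Hypothesis 2. Section 8.2.1 lists the annualised observed change first, and at an odd visit that change would naturally end earlier. Section 8.2 is headed as examples. The principal eGFR in Section 6.2.1.3.3 comes from a 2012 publication whose title names cystatin C, and the bedside value is reported in addition. The documents do not show whether the 2012 equation contains height. Before the 2016 amendment all Cohort 1 and 2 participants had iohexol GFR. Height is also measured at every visit, so growth can be analysed against iohexol visits. All of this stands, and it limits the point to analyses that use the creatinine option.

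The objection on size also stands in part. The 0.55 and 0.70 constants belong to a formula that Section 6.2.1.3.2 says overestimates iohexol GFR, and the step applies to boys only. Because G is a within-child change, a constant proportional height deficit largely cancels; only height change within the interval matters.

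Finally, Section 6.2.1.3.3 reports that eGFR and iohexol GFR give the same inferences, "with most markers having a stronger relationship with eGFR than iGFR", and height z-score is among those markers. That is a relevant check and should be kept. It does not test a model in which GFR change and height share a visit.

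**Conclusion.** The point holds as a badly specified exposure. The text allows a same-visit creatinine estimate, the printed formulas contain height, and the observed-GFR alternative has become unavailable for most children. At fixed creatinine and an assumed 3-7% height gain, the artefact is about 1.7 to 4.1 ml/min/1.73m² at 58. It is zero if creatinine rises in proportion to height and reverses if creatinine rises faster. The 21% fall is an upper illustration for boys under superseded constants.

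A reader might infer that the growth questions cannot be answered in either direction. The documents do not support that: iohexol GFR remains permitted, and the bias can be nil. Nor can the 274 of 586 Cohort 1 children enrolled at 11-16 years be taken as the number affected, since that count includes girls and boys already past 13.

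**What to change.** In Sections 8.2.3 and 6.5.3, and for the accelerated-growth term of Hypothesis 2:
- Do not use a same-visit, height-based eGFR as the main exposure or outcome.
- Use one measure without the height/creatinine ratio at both ends of each child's GFR change: iohexol at both, or cystatin C alone at both. Mixing them would put a change of method inside G. Cystatin C is already collected; Section 6.2.1.4 says "We will include each of these measures at baseline and at all annual study visits".
- Allow for the different laboratory that measured Cohort 1 baseline cystatin C (Section 3.4), with an indicator or by starting from central-laboratory values.
- End the GFR interval before the growth interval, as Sections 5.4.1 and 6.5.3 state.
- Adjust for Tanner stage. Section 2 lists delayed puberty among the effects of kidney failure, so show results with and without this adjustment.
- Keep the height/creatinine eGFR as a sensitivity analysis.
- Correct the GFR cross-reference in Section 8.2.3 from 8.2.2 to 8.2.1.
- Keep the height z-score comparison in Section 6.2.1.3.3, but do not cite it in support of the change model.

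The cost is wording and re-analysis, with no new samples. Cystatin C alone may be less precise. Lagging the exposure gives up the earliest growth interval. Iohexol GFR is scaled to body surface area (Section 6.2.1.1), so it is not wholly free of body size.

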## 5.4.2 Irregular Study Visits (previously referred to as Accelerated Study Visits)

The CKiD protocol includes irregular study visits for children with a high probability of reaching ESRD within the calendar year following a study visit, children who are scheduled for renal replacement therapy before their next study visit or children who are moving outside of the CKiD area, transitioning to adult care or other long-term factors which prevent the participant from returning to a participating CKiD site. The rationale for irregular study visits in these children is to attempt to capture the clinically relevant changes in exposures at low levels of GFR, but before the onset of renal replacement therapy and to obtain clinically relevant data on a population who will be unable to complete regular study visits at participating sites.

These children will have their next study visit accelerated from 12 months in the future to within 3 months of the scheduled renal replacement therapy initiation. Irregular study visits will consist of the collection of cardiac MRI data (if applicable) and the next consecutive study visit (i.e., a CVD visit or a NC/Growth visit). Iohexol GFR data will not be collected. Also, if the cardiac MRI data cannot be obtained during the scheduled irregular visit, the measurements should be obtained prior to initiation of RRT. Furthermore, in instances when the next consecutive visit is a NC/Growth visit, the child will receive a modified NC. Also, laboratory values collected during the irregular visit will be used to calculate an estimated GFR.

For children requiring an irregular study visit, the irregular visit will be a CKiD study visit prior to beginning the Post Renal Replacement Therapy or Continued Follow-up protocol. In the event that the renal replacement therapy is not initiated or other reasons specified above (i.e., transition to adult care) do not happen after the irregular visit has occurred, then the participant will return to completing regular CKiD study visits.

#### 5.4.3 Continued Follow-up Protocol

Participants will be given the option to participate in the continued follow-up protocol after they have renal replacement therapy, pregnancy, unable to reach or withdrawal (i.e., lost to regular follow-up). However, children who have a cancer diagnosis will be ineligible to participate in the follow-up protocol. The follow-up protocol will be composed of two components: an interview/survey and chart review. For convenience, the follow-up interview/survey will be completed via phone, in-person interview, mail or on-line. During the interview/survey, renal therapy status data will be obtained. Additional data such as sociodemographic information, medical history, health care utilization status, medication use, physical symptoms and quality of life data may also be collected. In conjunction with the follow-up interview/survey, the coordinator will collect data (i.e., lab results) from chart review to ascertain accurate data and the data may be reviewed by a researcher selected by the CKiD study who is not affiliated with the clinical site. Ideally, the follow-up protocol should be scheduled to occur annually based on the anniversary date of the participant's baseline (V1a) visit (± two months). However, for participants who disenrolled prior to the addition of the follow-up protocol, their first follow-up will be completed as soon as possible and the subsequent follow-up interviews/surveys will occur annually based on the anniversary baseline (V1a) date (± two months).

